#### 8.2.2 Chemotherapy treatment schedule

Chemotherapy should start between 4 and 8 weeks after RT completion.

Chemotherapy is scheduled at 6-weekly intervals (+ 1-week for unavoidable delays, bank holidays etc.) for a maximum of 6 cycles (depending on tolerability) or until disease progression, whichever is sooner. Patients should be treated according to this schedule, as per standard practice.

It is recommended that initial doses (in the absence of renal or hepatic impairment) will be:

**Lomustine** 100mg/m^2, with dose banding/ capping as per the institution's usual practice day 1, PO, on a 42 day cycle, for up to 6 cycles.

**Procarbazine** 100mg/m^2, with dose banding/ capping as per the institution's usual practice once daily on days 1-10 or days 2-11, PO, on a 42 day cycle, for up to 6 cycles.

**Vincristine** 1.4-1.5mg/m^2 (or flat dose of 2mg if this is usual institutional practice), with dose banding/ capping as per the institution's usual practice IV, day 1, on a 42 day cycle for up to 6 cycles. If a patient has a body surface area (BSA) of <1.45m^2, then dosing must be based on BSA.

#### Tests required within 7 days prior to Cycle 1 and within 3 days of subsequent cycles:

Full blood count (FBC), urea and electrolytes (U&Es), liver function tests (LFTs).

Required haematological parameters to proceed with chemotherapy are: - Hb  $\geq$ 10 g/L (may be corrected with transfusion if necessary),

- Platelets  $\geq 100 \times 10^{9}/L$ ,
- Absolute neutrophil count  $\geq 1.5 \times 10^{9}/L$ ,
- White cell count  $\geq 3.0 \times 10^9$ /L,

Usual practice may be followed in terms of dose modifications for baseline renal or hepatic abnormalities or subsequent haematological toxicity, hepatic or renal dysfunction or pulmonary, neurological or other toxicity. The following guidelines may be helpful if local policies do not exist:

Dose recommendations for anticancer drugs in patients with renal or hepatic impairment (and associated appendices). Lancet Oncol 2019; 20: e200–07 (Krens *et al.* 2019)

South West Clinical Network. PCV: Procarbazine, Lomustine and Vincristine. https://www.swagcanceralliance.nhs.uk/wp-content/uploads/2020/09/PCV-v2.pdf (South West Clinical Network 2014)

BC Cancer Monographs for individual drugs: http://www.bccancer.bc.ca/health-professionals/clinical-resources/cancer-drug-manual/drug-index (BC Cancer)

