# 9.6 Chemotherapy pre-treatment assessments

Participants may start PCV chemotherapy at any time between 4 and 8 weeks post-end of RT. Participants will be reviewed prior to each cycle of adjuvant PCV chemotherapy. A clinical assessment should be performed within 7 days prior to Day 1 of each cycle of chemotherapy and blood tests should be performed within 7 days prior to Day 1 of cycle 1 and within 3 days of all subsequent cycles of PCV chemotherapy. Data collected will include (but will not be limited to):

Within 7 days prior to Day 1 of cycle 1 and within 3 days of Day 1 for all subsequent cycles:

 FBC, U&Es, LFTs, creatinine clearance and bilirubin (within required parameters to proceed with chemotherapy, see section 8.2.2 Chemotherapy treatment schedule for further details)

Within 7 days prior to Day 1 of each chemotherapy cycle:

- Confirmed that they are not pregnant with their doctor/treatment team.
- Clinical assessment (including participant's weight, clinical examination including CNS examination, documentation of concurrent medications of interest (including review of steroid use, anti-epileptics and hormonal therapies) and assessment of KPS)

The following will also be performed and recorded:

- Date treatment started and ended
- Chemotherapy dose details (any delays, dose reductions or interruptions that have occurred and the reason(s) for these)
- Toxicities using CTCAE

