# Table B2 Common Expected Side Effects for Lomustine (BC Cancer 2018),Procarbazine (BC Cancer, 2011) and Vincristine (BC Cancer, 2022)

Lomustine – Marrow toxicity may be delayed or prolonged.

These drugs may also cause alterations in liver function tests.

Less common but potentially severe side effects from PCV include: pneumontitis/ pulmonary fibrosis (acute or delayed), nephrotoxicity, secondary leukaemia or myelodysplastic syndrome, hypersensitivity, haemolytic anaemia, thromboembolism, myocardial infarction, SIADH (Syndrome of Inappropriate Anti-diuretic Hormone secretion), gastrointestinal tract perforation, pancreatitis.

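### The haemoglobin required before each PCV cycle is printed as at least 10 g/L (1 g/dL), most likely a slip for 100 g/L (10 g/dL)

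*Protocol*

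**What the plan says.** Section 8.2.2 of the protocol sets out PCV dosing and then, under the heading "Tests required within 7 days prior to Cycle 1 and within 3 days of subsequent cycles", names the blood tests to be done. A list follows, introduced by "Required haematological parameters to proceed with chemotherapy are". Its first entry is haemoglobin, with a minimum of "10 g/L (may be corrected with transfusion if necessary"). The next three entries are platelets (at least 100 × 10⁹/L), neutrophils (at least 1.5 × 10⁹/L) and white cells (at least 3.0 × 10⁹/L).

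Section 9.6 repeats the blood tests before each cycle and asks that results be "within required parameters to proceed with chemotherapy", referring the reader to section 8.2.2. It gives no haemoglobin figure of its own.

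After the list, section 8.2.2 adds: "Usual practice may be followed in terms of dose modifications for baseline renal or hepatic abnormalities". The same sentence extends that freedom to later haematological and other toxicity, and outside guidance is offered for sites without a local policy.

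Table B2 in Appendix B marks myelosuppression as an expected effect of all three drugs and says of lomustine: "Marrow toxicity may be delayed or prolonged".

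**The concern.** A haemoglobin of 10 g/L is 1 g/dL, which is not a workable lower limit for a patient attending as an outpatient. Read literally, the criterion would exclude practically nobody. It also makes the transfusion allowance pointless, since that allowance only has a use if some patients are expected to fall below the limit. The figure and its unit cannot both be what the authors meant.

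This is a patient-safety matter. It is the only red-cell criterion among the conditions for starting a cycle, and the drugs are expected to suppress the marrow. The protocol also treats PCV as part of the trial treatment: section 10.1.2 defines trial treatment as radiotherapy together with adjuvant chemotherapy. Section 9.20 requires protocol violations to be entered within 24 hours of the site becoming aware. Against the printed figure, a cycle given at a haemoglobin of 70 g/L complies with the protocol, so there is nothing to flag.

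**Working it through.** No sample size, power or alpha figure is involved. The check is a unit conversion and a search for a correcting statement.

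**1. The printed value.** Since 1 g/dL = 10 g/L, a limit of 10 g/L is 10 / 10 = 1 g/dL.

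**2. Whether that can be intended.** Two statements in the protocol argue against it.
- The line itself allows correction by transfusion, which presupposes a limit that patients in the trial may fail.
- Section 4.1 requires a Karnofsky score of at least 70% at entry, and PCV is given to patients well enough to be reviewed in clinic before each cycle. Such patients do not present at 1 g/dL.

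**3. Likely intended value.** Two simple slips would explain the text.
- Wrong unit: 10 g/dL was meant, and 10 × 10 = 100 g/L.
- Lost zero: 100 g/L was meant directly.

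Both give 100 g/L, so the proposed correction does not depend on which occurred. The ratio of intended to printed limit is 100 / 10 = 10.

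**4. Results wrongly passed.** If the limit is 100 g/L, whole-number results from 10 to 99 g/L pass as printed but should be held or transfused. If the clinical team meant some other limit T, the band runs from 10 g/L to just below T. The protocol does not state T, so 100 g/L remains an assumption.

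**5. Whether another section repairs it.**

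| Place in protocol | What it says on haemoglobin |
|---|---|
| 8.2.2, list of limits | at least 10 g/L, transfusion allowed |
| 8.2.2, other three limits | platelets, neutrophils, white cells; none covers red cells |
| 8.2.2, local practice | dose modification only; no haemoglobin value |
| 9.6 | refers back to 8.2.2; no value |
| Appendix B, Table B2 | myelosuppression expected; no limit |

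No section supplies a haemoglobin value that would override the printed one.

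**6. How often the line is applied.** All 246 patients are to receive PCV, for at most 6 cycles, so the line governs at most 246 × 6 = 1,476 decisions to proceed. That is the ceiling on how often the criterion is used, not an estimate of harm. The number of decisions that would change cannot be computed, because the protocol gives no anaemia rate.

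**The case against.** Four points can be made on the other side.

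*Local practice governs PCV.* Chemotherapy is standard of care, section 8.2.2 allows usual practice and names outside guidance, and section 10.3.3 leaves toxicity and dose modification to local guidelines. This stands in part: a clinician who spots the error has somewhere to look. But those statements concern dose modification and toxicity management. The limits for proceeding are listed separately and described as required, and nothing replaces them. Centres falling back on their own figures (18-25 are planned) may not choose the same one.

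*Clinicians will notice.* Probably so, and this limits the practical risk. A full blood count and clinical assessment precede every cycle, section 4.1 requires that there be no known haematological impairment making PCV inappropriate, and the other three count limits are sound. It does not make the printed criterion right.

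*The comparison is unaffected.* This stands. The same PCV criterion applies in both arms, and the slip does not touch the primary endpoint, sample size or error rates.

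*The figure may have been damaged when the text was read from PDF.* The haemoglobin item runs on from its introductory sentence while the other limits are separate bullets, and there are misread characters elsewhere. A lost zero is therefore possible. It is not indicated, because the line reads cleanly and the neighbouring values, including 100 for platelets, are intact. The sponsor can settle it at once by looking at the source page.

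**Conclusion.** The concern holds. The haemoglobin criterion in section 8.2.2 is wrong as written: 10 g/L equals 1 g/dL, which cannot be meant beside a transfusion allowance, and nothing elsewhere corrects it. If the intended limit is 100 g/L, the printed figure is too low by a factor of ten and values from 10 to 99 g/L pass when they should not. That intended value is inferred, and the conclusion assumes that the text at hand reproduces the protocol page faithfully. The error is in a clinical threshold and does not reach the trial's statistical design. It should be fixed because it concerns a safety condition applied before every cycle of a trial treatment.

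**What to change.** Correct the haemoglobin line in section 8.2.2 to the intended limit, apparently at least 100 g/L (10 g/dL). Printing both units would prevent a repeat. The clinical team must confirm the value first, since the protocol offers no second figure to check against. Notify sites without waiting for other changes.

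A separate editorial point can go into the same amendment. Section 9.6 refers to section 8.2.2 for required parameters in a line that also names creatinine clearance and bilirubin, for which section 8.2.2 sets no limits. Reword it to refer to section 8.2.2 for the haematological limits and to local practice for the other two.

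The cost is low: a one-line correction in the next amendment and a notice to sites.

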# For each cycle of chemotherapy, the pre-treatment clinical assessment must be performed within 7 days prior to Day 1 of each cycle.

## 8.2.3 Supportive medications, pre-medications and dietary advice

Anti-emetics and other supportive measures, such as dexamethasone, may be prescribed as per each institution's usual practice.

Constipation is common with vincristine - laxatives are recommended on a PRN basis for all patients.

For patients receiving procarbazine, dietary advice should be provided as per each institution's usual practice.

Granulocyte colony stimulating factor (GCSF) may be used as per usual hospital practice. Of note, concurrent use of GCSF and vincristine may result in severe neuropathy. Ideally GCSF should be avoided within 5 days of vincristine administration unless the clinical benefits (e.g. in cases of severe neuropenic sepsis) are considered to outweigh the risks.

#### Precautions

Neutropenia may occur: fever or other evidence of infection should be assessed rapidly and managed in line with institutional policy for neutropenic sepsis.

For patients receiving Lomustine, a vomited dose of Lomustine should not be repeated if it occurs more than 30 minutes after administration.

A vomited dose of procarbazine should not be repeated.

Hypersensitivity (to procarbazine) should be managed according to local hospital guidelines.

Women of child-bearing potential or men who are sexually active must use medically acceptable forms of contraception, see section 4.3 Birth control: contraception and pregnancy testing.

#### Missed doses

A missed dose of lomustine may be taken any time on the day that it is due. Doses of Lomustine that are missed for more than three days should be omitted.

A missed dose of procarbazine may be taken within 8 hours of the time it is due. A dose that has been missed for more than 8 hours should be omitted. The next dose should be taken on schedule. Doses should not be doubled up to make up for missed doses.

## Overdoses of trial medication

A dose of Lomustine, Procarbazine or Vincristine in excess of that specified according to the protocol will constitute an overdose.

## Medications to be avoided and drug interactions

All concomitant medications including any over the counter or complementary treatments should be reviewed and potential interactions considered.

Live vaccines should be avoided during and for 6 weeks after completion of chemotherapy.

Where particular medications should be avoided (see list below), necessary washout periods and required intervals to re-starting these agents, should be discussed with the local Pharmacy team.

# LOMUSTINE:

- Cimetidine (enhances toxicity of lomustine): avoid
- Alcohol: avoid on the day that lomustine is taken
- Theophylline medications: avoid
- Anti-epileptics check with your Pharmacist there may be pharmacokinetic interactions depending on agent

#### **PROCARBAZINE:**

- Alcohol or tyramine containing foods (can result in nausea, vomiting, CNS depression, hypertension (including hypertensive crisis), changes in vision and headache): avoid.
   Dietary advice regarding foods that should be avoided should be as per the institution's usual practice for patients taking procarbazine
- Antihistamines (can result in increased CNS or respiratory depression): use with caution
- Levodopa (concurrent use causes hypertension): avoid concurrent use
- Tricyclic anti-depressants and other mono-amine oxidase inhibitors (concurrent use can cause CNS excitation, hypertension, tremors, palpitations, hypertension (including hypertensive crisis) or angina: avoid concurrent use
- Anti-diabetic agents: concurrent use may worsen hypoglycaemia: close monitoring of blood sugars required
- Anti-epileptics check with your Pharmacist there may be pharmacokinetic interactions depending on agent

# VINCRISTINE:

- Itraconazole: avoid
- Drugs that inhibit drug metabolism via cytochrome P450: avoid
- Phenytoin: vincristine reduces plasma levels: monitor for effect
- Digoxin: vincristine reduces plasma levels: monitor for effect
- Filgrastim (GCSF): concurrent use may result in severe neuropathy: avoid within 5 days of vincristine administration unless the clinical benefits (e.g. in cases of severe neutropenic sepsis) are considered to outweigh the risks.

# 8.4 Withdrawal of treatment or data collection

In line with usual clinical care, cessation or alteration of treatment at any time will be at the discretion of the attending clinician or the participant themselves. If a clinician withdraws a participant or if a participant withdraws consent for further trial treatment and/or further collection of data, their data and any samples collected prior to withdrawal of consent will remain on file and will be included in the final study analysis. Data outstanding up to the point of withdrawal will be chased with site.

The PI, or delegate should make every effort to ensure that the specific wishes of any participant who wishes to withdraw consent for further involvement in the trial are defined and documented using the Withdrawal eCRF, in order that the correct processes are followed by the CTRU and site following the withdrawal of consent.

In addition, it is suggested that the participant is made aware of the fact that if any significant new information becomes available concerning the treatment they have received in the trial, it may be necessary to contact them in the future.

# 9 Assessments

# 9.1 Eligibility assessments

The following investigations and assessments must be carried out prior to randomisation and can be used to establish eligibility.

All investigations and assessments that are listed below and carried out before consent for APPROACH can be considered standard of care, with the exception of the pregnancy screen, which has a separate consent process (see section 7.2 Recruitment and informed consent).

No specific time limit prior to randomisation:

• Diagnostic biopsy or surgery to gain histology

Within 7 days prior to randomisation:

Confirmed that they are not pregnant with their doctor/treatment team. Since this is
an eligibility criteria and must be performed prior to consent, participants of childbearing potential must consent using the shortened pregnancy eligibility screening
PISICF, to being pregnancy screened and potentially being required to show a
negative pregnancy result prior to consenting to the trial.

Within 14 days prior to randomisation:

- KPS
- Medical history
- Clinical assessment (including participant's height and weight, clinical examination including central nervous system (CNS) examination and documentation of concurrent medications of interest (including review of steroid use, anti-epileptics and hormonal therapies))

In addition, completion of the baseline neurocognitive function (NCF) tests MUST take place prior to randomisation (see section 9.10 Neurocognitive function tests).

# 9.2 Pre-randomisation/Baseline assessments

In addition to the above eligibility assessments, data collected on the pre-randomisation eCRFs (Baseline and Randomisation), will also include (but will not be limited to):

- Participant details and demographics including sex, date of birth, date of diagnosis of ODG, previous interventions for ODG (biopsy only or subtotal or gross total resection) and date of interventions
- Confirmation of written informed consent
- Completion date of baseline neurocognitive testing
- Confirmation of completion of HRQoL and related questionnaires (EORTC QLQ-C30 and BN20, EQ-5D-5L, MFI, HADS, WPAI, additional health resource use questionnaire), Caregiver Needs Screen
- Confirmation of the date of an up-to-date MRI scan, performed within 28 days prior to randomisation to serve as the baseline scan to assess response rates and progression-free survival
- Baseline CTCAE symptom scores
- Caregiver baseline data
- Baseline MRI: randomisation must be performed within 28 days of the magnetic resonance imaging (MRI) that leads to the decision that RT is required at that point

in time. Outside of 28 days, an updated MRI is required to serve as a contemporaneous baseline scan to assess response to further treatment

The following HRQoL questionnaires should also be completed pre-randomisation by both the participant and, if willing and consent obtained, their primary caregiver on the paper baseline QoL booklet provided by CTRU in clinic:

- EORTC QLQ-C30 and BN20 (completed by participant)
- EQ-5D-5L (completed by participant)
- Multi-dimensional Fatigue Inventory (MFI) (completed by participant)
- Hospital and Anxiety Depression Scale (HADS) (completed by participant)
- Work Productivity and Activity Impairment (WPAI) and an additional health resource use questionnaire (completed by participant and primary caregiver)
- Caregiver Needs Screen questionnaire (completed by primary caregiver)

Please see section 9.12 Participant and caregiver questionnaires below for further details.

## 9.3 Pre-treatment assessments

Data collected following randomisation but prior to the RT treatment start date will include (but will not be limited to):

Within 7 days prior to CT simulation for RT:

• Confirmed that they are not pregnant with their doctor/treatment team.

Within 7 days prior to start of RT:

• Confirmed that they are not pregnant with their doctor/treatment team.

Within 21 days prior to start of RT:

• CT simulation scan for RT planning

In addition:

MRI to assist in radiotherapy planning: this is performed ideally within 21 days, but **must** be performed within 28 days, of the CT simulation scan

Completion date of endocrine assessments (see section 9.11 Endocrine testing) will be collected on the Endocrine Assessment eCRF. Must be completed between randomisation and start of radiotherapy, ideally within 4 weeks of randomisation.

After randomisation and before starting PBT or photon RT, discontinuation of any radiosensitisers must be documented.

#### 9.4 Weekly assessments during PBT or photon RT

Participants should be seen once weekly for review and assessed clinically for symptoms and toxicity, together with documentation of concurrent medications of interest (including review of steroid use, anti-epileptics and hormonal therapies) and assessment of performance status. These may be performed in the formal outpatients' clinic or as 'on-treatment' reviews. Toxicities will be assessed based on the latest National Cancer Institute Common Terminology Criteria for Adverse Events (NCI-CTCAE v5.0). A copy of the NCI-CTCAE is provided in the ISF.

Details of PBT or photon RT treatment will be collected on a weekly basis by completing the PBT Treatment or Photon RT eCRFs. Data collected during these visits will include (but will not be limited to):

- Date treatment started and ended
- Weekly number of fractions and weekly doses given
- Details of any interruptions, including reason(s)
- For patients who are randomised to PBT, any fractions delivered as photon RT, the number of photon fractions delivered and the reasons for this
- Clinical assessment (clinical examination including CNS examination, documentation of concurrent medications of interest (including review of steroid use, anti-epileptics and hormonal therapies) and assessment of KPS)
- Acute toxicity scores for adverse reactions (ARs) related to treatment using CTCAE

## 9.5 Assessments during final week of PBT or photon RT

The following assessments should be completed on any day the participant receives one of their 5 final radiotherapy treatments (i.e. during their final week of treatment). Data collected will include (but will not be limited to):

- As per the weekly assessment above and:
- HRQoL questionnaires (EORTC QLQ-C30, EORTC BN20, EQ-5D-5L, MFI and HADS (completed by participant)),
- WPAI questionnaire and additional health resource use questionnaire (completed by participant and primary caregiver),
- Caregiver Needs Screen questionnaire (completed by primary caregiver).

# 9.6 Chemotherapy pre-treatment assessments

Participants may start PCV chemotherapy at any time between 4 and 8 weeks post-end of RT. Participants will be reviewed prior to each cycle of adjuvant PCV chemotherapy. A clinical assessment should be performed within 7 days prior to Day 1 of each cycle of chemotherapy and blood tests should be performed within 7 days prior to Day 1 of cycle 1 and within 3 days of all subsequent cycles of PCV chemotherapy. Data collected will include (but will not be limited to):

Within 7 days prior to Day 1 of cycle 1 and within 3 days of Day 1 for all subsequent cycles:

 FBC, U&Es, LFTs, creatinine clearance and bilirubin (within required parameters to proceed with chemotherapy, see section 8.2.2 Chemotherapy treatment schedule for further details)

Within 7 days prior to Day 1 of each chemotherapy cycle:

- Confirmed that they are not pregnant with their doctor/treatment team.
- Clinical assessment (including participant's weight, clinical examination including CNS examination, documentation of concurrent medications of interest (including review of steroid use, anti-epileptics and hormonal therapies) and assessment of KPS)

The following will also be performed and recorded:

- Date treatment started and ended
- Chemotherapy dose details (any delays, dose reductions or interruptions that have occurred and the reason(s) for these)
- Toxicities using CTCAE

